- 2. To study safety, tolerability and quality of life in the trial period of liraglutide vs placebo application
- 3. To collect first data about the efficacy of a liraglutide therapy in patients with an ileo-anal pouch anastomosis (IPAA) and abnormal high bowel frequency in the absence of inflammation for planning a larger phase 3 study in this orphan status patient population

STUDY DESIGN

Randomized, double-blind, 2-period, placebo- controlled, crossover proof of concept study. Ten patients with increased bowel frequency is defined as > 8 bowel daily/week without significant pouchitis* will be randomized to either liraglutide or placebo treatment for 6 weeks (Period 1). Subjects will be randomized 1:1 to 1 of 2 treatment sequences, liraglutide-placebo or placebo-liraglutide, and receive either liraglutide or volume-matched placebo. After a washout period of at least 5 days (the half-life of liraglutide is 11-12 hours, thus the minimal washout period of 5 days is equal to 10 half-life's) patients will be crossed over to the other treatment arm (Period 2). Since high bowel frequency can result in significant malaise and dehydration, patients not responding to the respective therapies in period 1 may be crossed over after 4 weeks of therapy or in period 2 can be terminated early at week 4. The rationale behind the early termination is based on 2 open label cohorts reporting the efficacy of liraglutide or exenatide in patients with high output ileostomies (the patient group the most comparable to the pouch patient population). GLP-1 receptor agonist therapy even at the lowest dose showed an almost immediate effect reducing the ostomy output after 1-3 days in most patients.^{26, 27} Thus, patients not responding to a 4-week therapy with a GLP-1receptor agonist are highly unlikely to respond if the therapy would be continued.

[figure not shown]

Figure 3: Study design

Randomization: Subjects will be randomized 1:1 to 1 of 2 treatment sequences, liraglutide—placebo or placebo—liraglutide, and receive either liraglutide or volume-matched placebo.

STUDY DRUG, SUPPLY OF STUDY DRUG AND RECRUITMENT PLAN

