 New start of biologics, antibiotics, steroids, anti-motility therapies (e.g. hyoscyamine, loperamide, atropine)

• Non - steroidal anti-inflammatories (NSAIDs) as long-term treatment, defined as use for at least 4 days a week each month

STUDY OUTCOMES

PRIMARY OUTCOME

Reduction of the mean of the 7-daily bowel frequency by 30% in week 4 and week 10.

SECONDARY OUTCOME

- Safety and Tolerability of GLP-1
 - Number of study patients, who discontinued therapy
 - Adverse events grouped by body system
 - Changes in laboratory values
 - Changes in nausea, appetite, abdominal pain and well being
- Change in bowel frequency during day (patient is awake from morning until bedtime) and during night (patient is asleep and has to get up because he has a bowel movement) comparing screening period to week 1, week 2, week 3 and week 4 during active treatment with liraglutide or placebo in period 1 or in period 2 (week 7, 8, 9 and 10).
- Change in clinical PDAI week 0 and week 4 and week 10

EXPLORATORY OUTCOMES

- Change in stool calprotectin from baseline
- Change in SF-36
- Change in PROMIS measures
- Change in PROBE score
- Change in body weight and experience of nausea, decreased appetite or increased abdominal pain
- Change in PDAI at week 6 or week 12 in patients responding to liraglutide therapy
- Change in bowel frequency during day (patient is awake from morning until bedtime) and during night (patient is asleep and has to get up because he has a bowel movement) comparing screening period to week 5 and 6 in period 1 or 11 or week 11 and 12 in period 2.

ASSESSMENTS/INDICES

In regard to when the assessments are performed please also refer to study visits and table study visits and assessments.

- Patient diary (performed daily): Bowel frequency during the day (6 am-6 pm) and night (6 pm -6 am) and recording of bowel movement consistency (liquid, pasty or formed)¹⁴
- Patient diary (performed daily): Timing of bowel movement in relation to meals (within 15 min, 30 min or >30 min)
- Modified pouch disease activity index (mPDAI)³⁵

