The Pouchitis Disease Activity Index (PDAI) was developed by Sandborn et al for diagnosing active pouchitis and quantifying the severity of pouchitis ³⁶. Shen et al. later on modified the index (mPDAI) and showed that similar outcomes can be measured after omitting the evaluation of histology, thus omitting the biopsy and histology costs. ³⁵ The PDAI or the modified PDAI has been used in a number of clinical studies where it appears quite useful in discriminating between subjects with and without pouchitis and in quantifying the severity of pouchitis ³⁷⁻⁴⁵ The mPDAI will be evaluated based at screening, week0,2,4,6,7,8,10,12.

- Stool calprotectin (assessment of pouch inflammation over time)
 Calprotectin, a member of the S100 family of calcium-binding proteins is abundant in the stool and its level correlates with the endoscopic degree of intestinal inflammation in patients with ulcerative colitis and pouchitis. 46,47 Calprotectin can be quantified in feces using enzyme-linked immunosorbent assay (ELISA) or an immunoassay. We will collect stool samples for the measurement of calprotectin at the screening visit and on weeks 2,4,6,8,10,12.
- 36-Item Short Form Health Survey (SF-36)
 The SF-36 will be evaluated at screening, week 2,4,6,8,10 and 12.
- PROMIS measures for incontinence⁴⁸

The GI-PROMIS scales belong to the PROMIS system, which was created by the National Institutes of Health (NIH) to allow efficient, online measurements of patient reported outcomes and correlate with other established quality of life measures.^{48, 49} The PROMIS scale for incontinence will be evaluated at screening, week 2,4,6,8,10 and 12.

- PROBE score⁵⁰
 - PROBE assesses the psychosocial burden of IBD and has been recently validated.⁵⁰ PROBE will be evaluated at screening, week 2,4,6,8,10 and 12.
- Body weight and visual analogue scales for nausea, appetite, abdominal pain and well being²⁵ Body weight will be evaluated at screening and on weeks 4,6,10,12.

OVERVIEW OF TRIAL SEQUENCE

Screening visit (site visit): The trial will begin with the screening visit (days -14 to -10). The investigator will ask patients who are interested in participating in the study after a careful explanation, to sign an informed consent form prior to study specific examinations. The study patient will receive a copy of the consent form, which outlines the sequence of events in brief and summarizes the advantages and disadvantages of participation in the study.

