The primary outcome is the reduction of the mean 7-day bowel frequency of 30% compared to baseline (baseline is defined as the mean 7-day bowel frequency in a 7-day period during the screening period before week 0). A crossover trial will be performed. Subjects with a history of averaging > 8 bowel movements per day over a 7-day span will be entered into the study and the

order in which they receive treatments (liraglutide or placebo) will be randomized. At the end of each week, the average number of bowel movements the subject had during that week will be computed. A repeated measure mixed model will be fit to the data with treatment (liraglutide or placebo), period and treatment sequence as fixed effects and the repeated measures within subject as a random effect. After the model is run, any non-significant effects for period or treatment sequence will be removed from the model. The treatment effect will remain in the model and is the outcome of interest. P-value less than 0.05 will be considered statistically significant. In a sensitivity analysis the same model will be run without removing any effects. P-value less than 0.05 will be considered statistically significant.

Secondary analyses

Continuous secondary outcomes (stool frequency, clinical PDAI) will be summarized using descriptive statistics (mean, median, standard deviation, minimum, and maximum) of the values at each assessment and the change from baseline to each assessment. A repeated measure mixed model will be fit to the data with treatment (liraglutide or placebo), period and treatment sequence as fixed effects and the repeated measures within subject as a random effect. After the model is run, any non-significant effects for period or treatment sequence will be removed from the model. The treatment effect will remain in the model and is the outcome of interest. P-value less than 0.05 will be considered statistically significant.

Safety analyses

The safety analyses will comprise all included patients, who got at least one dose of the investigational product.

- Number of study patients, who discontinued therapy
- Adverse events grouped by body system
- Changes in laboratory values

Exploratory analyses

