We will perform exploratory analyses using descriptive statistics (mean, median, standard deviation, minimum, and maximum) and bivariate analyses of the values at each assessment and the change from baseline to each assessment. In the evaluation of the PROMIS measure for incontinence, PROMIS measures utilize a T-score metric where a score of 50 is the mean of a relevant reference population and 10 is the standard deviation. Additionally, a clinically minimally important difference is reflected by a change of 2.

Missing data

Due to short and intensive period of follow-up for the primary outcome, we do not anticipate significant missing data.

SAMPLE SIZE CALCULATION

The analysis will be based on the within-subject difference between two one-week averages of the number of bowel movements per day (BMPD). A one-sample t-test will be used to test the

null hypothesis that the mean difference is zero. With a sample size of 10 subjects and Type-I 0.05 (2-sided), the power is 0.80 against a difference of 1 standard deviation (SD) of the difference (not SD of the individual outcomes). The first average within each patient, by design, will be greater than 8 BMPD, and the range is most likely to be 8-11. The standard deviation (SD) of such an outcome can't (mathematically) exceed 1.5, and this will be used in the sample size calculations as the SD of each weekly average (control and treatment). Additionally, the SD of the difference depends on the correlation between the two weekly averages. Taking that into account, the power is 0.80 against a difference of 2.1 BMPD if the correlation is 0, 1.8 BMPD if the correlation is 0.25, 1.5 BMPD if the correlation is 0.50, 1.1 BMPD if the correlation is 0.75. Assuming a baseline average of 10 BMPD, the design has good power against relative changes of 21% or higher if the within-subject correlation is zero. The power increases with increasing positive correlation and, naturally, is higher against larger effects. If patients drop out during the study the power will decrease, however patents will be carefully selected and thus dropouts are unlikely to occur.

FUTURE PERSPECTIVE

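### No within-patient liraglutide-minus-placebo comparison is specified for quality of life, calprotectin or body weight, because the crossover model is not extended to the exploratory outcomes

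*Combined protocol and SAP*

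**What the plan says.** STUDY AIMS, Aim 2: "To study safety, tolerability and quality of life in the trial period of liraglutide vs placebo application".

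STUDY DESIGN: a two-period crossover. "Ten patients with increased bowel frequency" are enrolled, and "Subjects will be randomized 1:1 to 1 of 2 treatment sequences, liraglutide-placebo or placebo-liraglutide". Blocking is not mentioned.

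STUDY OUTCOMES places SF-36, PROMIS, PROBE, calprotectin ("Change in stool calprotectin from baseline") and weight ("Change in body weight and experience of nausea, decreased appetite or increased abdominal pain") under exploratory outcomes.

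ASSESSMENTS/INDICES: "The SF-36 will be evaluated at screening, week 2,4,6,8,10 and 12". PROMIS, PROBE and calprotectin follow the same weeks. Body weight is scheduled at screening and weeks 4, 6, 10 and 12.

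DATA ANALYSIS treats the two groups of outcomes differently:
- Primary and continuous secondary outcomes (the latter named as stool frequency and clinical PDAI): "A repeated measure mixed model will be fit to the data with treatment (liraglutide or placebo), period and treatment sequence as fixed effects", with a within-subject random effect.
- Exploratory outcomes: descriptive statistics and "bivariate analyses of the values at each assessment and the change from baseline to each assessment". No test is named, the two variables are not identified, and treatment arm is not mentioned.

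**The concern.** The strength of a crossover is that each patient supplies both a liraglutide value and a placebo value. The plan uses this for bowel frequency and clinical PDAI. For the scales that answer the quality-of-life part of Aim 2, it names no analysis that does so.

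The wording is tied to each assessment. Weeks 2, 4 and 6 fall in period 1 and weeks 8, 10 and 12 in period 2, so at any one assessment a patient is on one treatment only. A treatment comparison made there sets one sequence group against the other. Taking change from baseline removes part of the between-patient variation but still compares different patients. It never sets liraglutide against placebo in the same person.

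Two things are at stake. One is precision, which is scarce with ten patients. The other is that, with no test named, the method for a stated aim could be chosen after the data are seen, over six post-baseline assessments per quality-of-life scale.

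**Working it through.** **Inputs.** From SAMPLE SIZE CALCULATION: n = 10, two-sided 0.05, power 0.80, SD 1.5 bowel movements per day (BMPD) for each weekly average, and correlations ρ of 0, 0.25, 0.50 and 0.75. From STUDY DESIGN: 1:1 allocation, taken here as 5 and 5. All power figures use the exact noncentral t distribution.

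**Step 1: reproduce the plan's figure.** One-sample t-test, n = 10, df = 9, difference of 1 SD of the difference: power is 0.803, against 0.80 stated. The difference detectable with 80% power is 0.996 × SD_diff, where SD_diff = 1.5 × √(2(1−ρ)). This gives 2.11, 1.83, 1.49 and 1.06 BMPD, against 2.1, 1.8, 1.5 and 1.1 stated. The plan's figures hold.

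**Step 2: the three possible treatment comparisons**, in units of the SD of a single value, each with df = 8:
- Values at one assessment, 5 v 5: SE = SD × √(2/5). The 80% detectable difference is 2.02 SD, whatever ρ is.
- Change from baseline at one assessment, 5 v 5: replace SD by SD × √(2(1−ρ)), assuming the same ρ between baseline and later values. Detectable: 2.024 × √(2(1−ρ)).
- Within-patient crossover analysis with a period term: SE = SD × √(2(1−ρ)) / √10. Detectable: 1.012 × √(2(1−ρ)).

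| ρ | 5 v 5, values | 5 v 5, change | Crossover |
|---|---|---|---|
| 0 | 2.02 SD | 2.86 SD | 1.43 SD |
| 0.25 | 2.02 SD | 2.48 SD | 1.24 SD |
| 0.50 | 2.02 SD | 2.02 SD | 1.01 SD |
| 0.75 | 2.02 SD | 1.43 SD | 0.72 SD |

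The variance of the 5 v 5 difference on values, relative to the crossover, is (2/5) / (2(1−ρ)/10) = 2/(1−ρ), that is 2, 2.7, 4 and 8. On change from baseline the ratio is (2/5)/(1/10) = 4 at every ρ, so the detectable difference is always twice that of the crossover.

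**Step 3: power for a 1-SD effect.** 5 v 5 on values: 0.29. Crossover: 0.50, 0.62, 0.79 and 0.97 at the four correlations. 5 v 5 on change at ρ = 0.75: 0.50.

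**Step 4: illustration on the plan's own bowel-frequency inputs.** At the stated differences of 2.1, 1.8, 1.5 and 1.1 BMPD, the crossover with a period term has power 0.78, 0.77, 0.79 and 0.82. A 5 v 5 comparison has 0.49, 0.39, 0.29 and 0.18 on values, and 0.28, 0.28, 0.29 and 0.30 on change.

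**Step 5: illustration for PROMIS.** Assume that the reference-population SD of 10 given under Exploratory analyses applies here. With t(8) = 2.306, the 95% CI half-width is 2.306 × 10 × √(2/5) = 14.6 points at 5 v 5 on values. For the crossover it is 2.306 × 10/√10 = 7.3 at ρ = 0.50, or 2.306 × 7.07/√10 = 5.2 at ρ = 0.75. The plan's minimally important change is 2, so neither analysis is powered for that.

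**Step 6: who is present at each assessment.** Under OVERVIEW OF TRIAL SEQUENCE, the week 6 visit of period 1 is for patients who did not cross over early at week 4. Week 10 non-responders have only adverse events and concomitant medication assessed at week 12 (footnote k of the visit table). At weeks 6 and 12 the comparison can therefore involve fewer than ten patients, selected by response. Weeks 4 and 10 come before both selections.

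**The case against.** The plan does not state a 5-versus-5 test. Bivariate could mean treatment by outcome, value against baseline, one outcome against another, or even a paired comparison. A reader might infer that the crossover is analysed as two parallel groups and the within-patient information thrown away. That is the likely reading of an analysis done at each assessment, but it is an inference; the text supports only that no within-patient treatment contrast is specified. A reader might also picture weeks pooled by treatment as 10 versus 10 independent observations. Nothing in the documents suggests this.

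Change from baseline is planned too and does use each patient's own starting value. At ρ = 0.75 it does clearly better than raw values (1.43 against 2.02 SD). At ρ = 0.50 it gives no gain, and below that it is worse.

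The outcomes are exploratory, in a ten-patient proof-of-concept study, and the sample size concerns bowel frequency only. It would go too far to say that a real benefit will be reported as no difference, or that a planned test is underpowered against a promise.

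These points limit the wording but leave the gap. Whichever meaning of bivariate was intended, the plan does not say how the quality-of-life comparison in Aim 2 will be made, and the better method already stands a few paragraphs earlier.

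**Conclusion.** The point holds as a gap in specification with a measurable cost in precision. No within-patient liraglutide-minus-placebo comparison is specified for SF-36, PROMIS, PROBE, calprotectin or weight. If arms are compared at one assessment, the detectable difference is 1.4 to 2.8 times that of the crossover on values (2.02/1.43 to 2.02/0.72), and twice on change from baseline.

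This rests on a split near 5 and 5, complete data, equal SDs in both periods, and the same correlation with baseline as between periods. The true correlations for these scales are not given, hence the range. It does not show that the sponsor has chosen a 5 v 5 test, nor that any stated power fails, because none is stated for these outcomes.

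**What to change.** Under Exploratory analyses, for treatment comparisons, replace the bivariate analyses with the mixed model already written for the secondary outcomes: treatment, period and sequence as fixed effects, patient as random effect. Keep all terms, as the primary sensitivity analysis does. With ten patients, a non-significant period or sequence term is weak grounds for dropping it.

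Take the week 4 and week 10 values as the main contrast. Both precede response-based early crossover or termination, both are scheduled for every scale and for weight, and they match the weeks of the primary outcome. Report the liraglutide-minus-placebo difference with a 95% CI for each outcome. Keep the by-week summaries, including weeks 2, 6, 8 and 12 where measured (weight has no week 2 or 8), as descriptive.

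The cost is a few lines of analysis text and one model fit per outcome. No new data, visits or patients are needed.

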POUCH PATIENTS AND THE PROBLEM OF BOWEL FREQUENCY

Increased bowel frequency interfering with daily activities presents a significant clinical problem for many pouch patients. Patients with a pouch typically have 4-8 bowel movements over 24 hours. ^{12, 13} However, a group of patients have a higher baseline bowel frequency in the range of 8-14 or higher bowel movements in a 24 hour period including increased nightly bowel frequency, incontinence and leakage, which significantly impacts their work and social life due to impaired sleep and need to alter the mealtimes. ^{14, 15} The reasons for a higher bowel frequency in patients with an otherwise not significantly inflamed pouch are thought to be due to hypermotility or pouch dysmotility. Thus far, no unique pathomechanism has been identified. Many patients report bowel movements which occur shortly after even small meals or especially after meals with a higher fat content. Currently, there are very limited medical options such as loperamide or anticholinergic drugs (dicyclomine) to control frequent bowel movements.

However, many patients do not respond to even extremely high doses of these medications or experience intolerable side effects (such as dry mouth or heart palpitations) while being on anticholinergic medications.

EFFECTS OF GUCAGON -LIKE PEPTIDES (GLP'S) ON GASTROINTESTINAL TRANSIT TIME AND BOWEL FREQUENCY

GLP-1 and GLP-2 belong to the group of incretins and are pleiotropic hormones that not only affect glucose metabolism (GLP-1) but also play a role in the regulation of gastrointestinal motility (GLP-1, GLP-2) and intestinal regeneration (GLP-2).^{16, 17} Other effects on intestinal biology such as impact on bile acid metabolism, anti-inflammatory properties or effects on the intestinal microbiome are currently debated.¹⁸⁻²⁰ GLP-1 prolongs gastric duodenal emptying and decreases gastrointestinal motility, whereas GLP-2 exerts a potential effect in intestinal weight gain, mucosal development, and intestinal integrity.^{18, 21} GLP- 1 and GLP-2 are simultaneously produced via posttranslational processing of proglucagon and are secreted by intestinal

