enteroendocrine L-cells after contact with ingested nutrients. Additionally, GLP-1 secretion occurs by α cells in the pancreas. L-cells are predominantly located in the distal ileum and colon. Absence or a decrease of these enteroendocrine cells leads to lower GLP-1 levels as well as lower levels of other incretins such as GLP-2 as shown in patients, who underwent colectomy and had a pouch or an ileo- or jeunostomys. ²²⁻²⁴ GLP-1 plasma levels increase especially after high fat meals in healthy volunteers, but only partially increase in patients with

[figure not shown]

Figure 2: Plasma GLP-1 following a starch-rich test meal and two subsequent high fat carbohydrate-free meals in control (\bigcirc) and ileostomist (\bigcirc) subjects. Values are means \pm s.e.m., n=6 for both groups.

ileostomy with less than 5 cm of terminal ileum resected (see Figure 2 from paper by Robertson et al. Journal of Endocrinology 1999)²³.

CLINICAL DATA

So far no threshold for sufficient postprandial GLP-1 levels have been described, but low levels of GLP-1 are associated with rapid small bowel transit in patients with a jejunostomy suggesting a defective neuro-endocrine "ileo-colonic brake" after removal of parts of ileum and/or colon. Application of GLP-1 or GLP-2 restores the transit time and decreases diarrhea and fecal excretions. Whereas the therapeutic efficacy of GLP-2 receptor agonist therapy e.g. with teduglutide for patients with short bowel syndrome is well established, two small studies in patients with ileostomies or short gut syndrome also suggest a clinical beneficial effect of a GLP-1 receptor agonist therapy. The GLP-1 receptor agonist liraglutide significantly reduced ileostomy output in a small group of 8 patients with high ileostomy output. In this study liraglutide reduced ostomy wet weight output by 474 ± 563 g/d from 3249 ± 1352 to 2775 ± 1187

g/d. Interestingly the effects were immediately evident in 3 patients after the start of therapy, whereas 2 patients were even after prolonged therapy non-responders explaining the high

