So far extent of tachyphylaxis of the effects of liraglutide on gastric emptying are inconclusive or not well defined. Liraglutide (1·2 mg, 1·8 mg, or 3·0 mg daily) delays 1-h gastric emptying, as measured by the plasma acetaminophen method (which reflects predominantly the gastric emptying of liquids, not solids) compared with placebo.³¹⁻³⁴ However, tachyphylaxis of the delay of gastric emptying seems to occur over time but the extent is not clear. For liraglutide 3.0 mg daily one study reports complete tachyphylaxis for delay in gastric emptying based on the plasma acetaminophen method after 5 weeks whereas another study, using a scintigraphy method for gastric emptying which includes the emptying of solid food describes partial tachyphylaxis but still significant efficacy compared to placebo after 16 weeks of therapy.^{32, 34} All studies so far have been performed in patients with an intact GI-tract. The question remains if tachyphylaxis occur in patients with low GLP-1 levels and potentially upregulated GLP-1 receptors in the absence of

a colon. In the only available 2 studies analyzing the effects of liraglutide or exenatide on jejunostomy output no tachyphylaxis was reported after 8 weeks(liraglutide) or 1 year (exenatide) of therapy.^{26, 27}

RECRUITMENT PLAN

We estimate to screen 20 - 25 pouch patients/month and randomize 1 patient/month. We expect that all patients will complete the study after randomization. Under the direction of [name], the University of North Carolina has a Multidisciplinary Pouch Clinic that involves gastroenterology and surgery care for pouch-related disorders. We follow approximately 450 patients from throughout the southeast region of the United States that are treated regularly in our clinic.

STUDY MILESTONES

Months	1-4	4-16	16-22
Activities	Start-up of	Recruitment	Follow-up last
	trial		patients
	IRB		Analysis of
	IND/FDA		clinical data

INCLUSION AND EXCLUSION CRITERIA

INCLUSION CRITERIA

- Informed consent will be obtained before any trial-related procedures
- Age > 18 years
- Patients with IPAA and bowel frequency > 8 bowel movements in 24 hours on at least 4
 of 7 days/week and presence of high bowel frequency > 4 weeks despite adequate
 therapy for acute pouchitis or Crohn's like disease of the pouch

EXCLUSION CRITERIA

- Significant pouch inflammation defined as an endoscopic pouch disease activity index
 (PDAI) ≥ 4

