Review of glucose diary and			Χ	X	Х	Х	Х	X	Х	Х		
hypoglycemic protocol and												
reporting form												
Assessment of response ^h					Χ				Х			
PROMIS questionnaires, SF36,	Х			Х	Х	Х		Х	Х	Х		
PROBE												
Study drug dispensation		Χ			X ⁱ	Χ						
Study drug collection										X^{j}		

^a Clinical PDAI excluding pouchoscopy

^bCBC, AST, ALT, AP, Bilirubin, Creatinine, CRP. Serum samples for GLP-1 baseline fasting if possible (Screening or week 0).

^c Subject diary will be maintained electronically and completed daily reporting stool frequency, rectal bleeding, fecal urgency or abdominal cramps, and/or fever. The patient will complete this diary each day, beginning with the screening visit and ending at the visit. The average 7-day bowel frequency will be calculated for each 7-day period. For the clinical PDAI scores the last three days of diary entries before each visit will be used to calculate stool frequency and fecal urgency/abdominal pain scores.

^d Phone visit only with review of diaries and dose increase of study drug if tolerated. Patient will mail stool sample calprotectin or bring in person.

^f Crossover occurs after at least 5 days of washout after the last study dose

^g Pregnancy test at week 4 in case of early crossover

h Assessment of response: If average weekly bowel frequency of patient did not decrease by at least 15% compared to baseline the patient can proceed to early crossover (Period 1 week 4) or early termination (Period 2 week 10).

Non-responder at Period 1 week 4 receive study drug for period 2 to start 5 days after the last study dose of period 1

^jCollection of study drug from non-responders in Period 2 week4 and all patients who were responding at Period 2 week 10 and completed study at Period 2 week 12.

^k For non-responders at Period 2 week 10 the safety outcomes below will be assessed at Period 2 week 12. For this patient group at Period 2 week 12 only adverse events (review adverse events diary) and concomitant medication will be assessed at Period 2 week 12. An alternative approach is a phone visit at Period 2 week 12 (similar to the final visit at Period 2 week 14) and patient returns all study medication from period 1 and 2 before Period 2 week 12.

REFERENCES

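### The SD of 1.5 is an assumption, not a mathematical maximum, so the stated power against a 21% change holds only if the SD of the within-patient difference is about 2.1 or less

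*Combined protocol and SAP*

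**What the plan says.** The Sample Size Calculation section bases the trial on a one-sample t-test of the within-patient difference between two weekly averages, with 10 patients and two-sided 0.05. It states power of 0.80 against a difference of one SD of that difference.

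To express this in BMPD it needs an SD for each weekly average. It reasons from a range: "The first average within each patient, by design, will be greater than 8 BMPD, and the range is most likely to be 8-11". The next sentence says that the SD of such an outcome cannot be larger than half that width: "mathematically) exceed 1.5, and this will be used in the sample size calculations as the SD of each weekly average (control and treatment". No data source is given for 1.5.

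From 1.5 it derives differences detectable with 0.80 power of 2.1, 1.8, 1.5 and 1.1 BMPD at correlations 0, 0.25, 0.50 and 0.75. With a baseline of 10 BMPD it concludes that "the design has good power against relative changes of 21% or higher if the within-subject correlation is zero".

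Two other places bear on the range. The background section on bowel frequency says that "a group of patients have a higher baseline bowel frequency in the range of 8-14 or higher bowel movements in a 24 hour period". The inclusion criterion sets a floor and no ceiling: "Patients with IPAA and bowel frequency > 8 bowel movements in 24 hours on at least 4" of 7 days. No exclusion criterion caps the frequency either.

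**The concern.** Half the width of an interval is the largest SD possible for values confined to it, so 1.5 is a true maximum for averages confined to 8-11. A range that is only most likely does not confine them. The plan's own background describes patients well above 11, and nothing in eligibility keeps them out.

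The range is also given for the first average alone, while 1.5 is applied to the treated week as well. The outcome that the trial aims for, "Reduction of the mean of the 7-daily bowel frequency by 30% in week 4 and week 10", would take a patient from 10 to 7 BMPD, outside 8-11. Leaving the interval does not by itself widen the spread, but the stated reason for the bound no longer covers that week.

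At stake is how the result is read. The 21% sentence appears to rest on a proven limit. If the SD of the difference exceeded about 2.1, power against 21% would be below 0.80, and a non-significant result in 10 patients could be over-read as evidence against an effect of that size. The study is meant to inform the planning of a larger trial, so that reading matters.

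**Working it through.** **Inputs.** From Sample Size Calculation: n = 10, two-sided 0.05, one-sample t-test, weekly SD 1.5, correlations 0 to 0.75, baseline 10 BMPD, so 21% is 2.1 BMPD. From Primary Outcome: the 30% target, so 3.0 BMPD. From the background: the range 8-14 or higher.

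**Formulas.** SD of the difference = s × √(2(1 − ρ)), where s is the weekly SD and ρ the correlation. Power comes from the noncentral t distribution with 9 degrees of freedom and noncentrality √10 × difference / SD of the difference.

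**1. The plan's own figures.** At one SD of the difference, power is 0.803 (stated 0.80). Power of exactly 0.80 needs 0.996 SD. With s = 1.5:

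| ρ | SD of difference | Detectable at 0.80 power | Plan states |
|---|---|---|---|
| 0 | 2.12 | 2.11 | 2.1 |
| 0.25 | 1.84 | 1.83 | 1.8 |
| 0.50 | 1.50 | 1.49 | 1.5 |
| 0.75 | 1.06 | 1.06 | 1.1 |

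All four reproduce.

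**2. Where 1.5 comes from.** (11 − 8)/2 = 1.5. The same bound for 8-14 is (14 − 8)/2 = 3.0. With no upper limit there is no bound.

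**3. The condition behind the 21% sentence.** The largest SD of the difference that keeps 0.80 power is 2.1/0.996 = 2.11 for a 21% change and 3.0/0.996 = 3.01 for the 30% target.

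**4. A moderate illustration.** Suppose weekly averages are spread uniformly over 8-14. The shape is an assumption; the range is the background's, without its open upper end. Then s = 6/√12 = 1.73, and the same SD is used for both weeks, as the plan does:

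| ρ | SD of difference | Power at 2.1 BMPD |
|---|---|---|
| 0 | 2.45 | 0.68 |
| 0.25 | 2.12 | 0.80 |
| 0.50 | 1.73 | 0.93 |

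So under this spread the 21% statement fails at zero correlation, the case for which the plan makes it, and holds from a correlation of about 0.25.

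**The case against.** The case for the plan is substantial.

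- **The condition is partly disclosed.** Power is stated per SD of the difference, and the 8-11 range stands in the sentence before the bound. This is true, and it limits the weight of the point. It does not rescue the claim of mathematical impossibility or its extension to the treated week.
- **The inputs are cautious within 8-11.** A uniform spread there has SD 3/√12 = 0.87, and zero correlation is the least favourable of the four cases shown. That stands, but only if the range holds.
- **A proportional effect would narrow the treated week.** If every patient falls by 21%, the treated SD is 1.5 × 0.79 = 1.19, the SD of the difference at zero correlation is √(1.5² + 1.19²) = 1.91, and power is 0.87. That also stands.

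A reader might go further and infer that the trial is underpowered. The documents do not support that. The 8-14 ceiling of 3.0 at zero correlation would give an SD of the difference of 4.24 and power of 0.29 at 2.1 BMPD, but it needs half the patients at 8 and half at 14. Nor do the documents supply a source for SDs of the difference such as 2.8 or 3.5. The one SD of change that they report, 563 g/d on a mean of 3249 in the liraglutide ileostomy study, scales to 563/3249 × 10 = 1.73 BMPD, where power at 2.1 is 0.93. That outcome is output weight, so the scaling is only indicative.

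A reader might also infer that a mix of responders and non-responders must push the SD past 2.1. The ileostomy study did report such a mix ("whereas 2 patients were even after prolonged therapy non-responders explaining the high" variation), but its SD of change already contains it; adding a mix to the plan's worst-case SD goes beyond that evidence. The 15% rule ("If average weekly bowel frequency of patient did not decrease by at least 15% compared to baseline the patient can proceed to early crossover") applies blind to both treatments and is no evidence of mixed response to liraglutide.

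**Conclusion.** The point holds as a correction to how an assumption is worded. Every figure in the calculation is right, but 1.5 is an assumed SD and is a maximum only if all averages in a week lie within 3 BMPD. The 21% statement therefore holds only if the SD of the within-patient difference is about 2.1 or less (taking good power to mean 0.80 and the baseline as 10 BMPD).

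The size is modest. Under the uniform 8-14 illustration, the shortfall at zero correlation is 0.68 against 0.80, and it disappears at a correlation of about 0.25. Power against the 30% target is at least 0.80 up to an SD of the difference of about 3.0. The point does not show that the trial is too small. It is at the low end of minor.

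**What to change.** Two sentences in Sample Size Calculation.

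1. Replace the claim of a mathematical maximum with: *We assume an SD of 1.5 for each weekly average, which is the maximum only if all averages in that week lie within an interval of 3 BMPD.*

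2. Replace the 21% sentence with: *Assuming a baseline of 10 BMPD, power is at least 0.80 against a 21% change if the SD of the within-patient difference is 2.1 or less, and at least 0.80 against the 30% target if it is 3.0 or less. For example, if weekly averages were spread uniformly over 8-14 (SD 1.73; the uniform shape is an assumption), power against 21% would be about 0.68, 0.80 and 0.93 at correlations 0, 0.25 and 0.50.*

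No further table of larger SDs is needed, since the documents give no source for them. The change adds no patients, visits or data and leaves sample size, design and analysis as they are. Its one cost is that the stated power becomes conditional and may look less favourable.
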